3.0 Objectives

- Describe the study's purpose, specific aims, or objectives.
- State the hypotheses to be tested.

In this study, we will test our model for the purpose of delineating the extent to which OAA can bring value to patient care in VHA. We plan to control for demographic factors, namely: age, sex, race, health literacy, and internet access. The project will be conducted in primary care and one specialty clinic: diabetes. We select diabetes because of its high prevalence in Veterans, the presence of a specific marker of disease control (Hgb A1C), and that disease management now relies on a growing number of medications and dietary interventions that can be complex and overwhelming for patients. OAA, hence, may offer substantial benefits to patients and their caregivers and, if it does, the effect should be captured by falling Hgb A1c levels among those with baseline poor disease control. As noted, we also plan to study the impact of OAA on uncontrolled BP, but that data can be collected entirely in primary care given the very high prevalence rate.

This study has three aims, with the first two designed to test measurable hypotheses. The third is qualitative:

Aim 1: Assess the impact of an open access audio program on two behaviors (patient activation, treatment plan adherence), and two chronic condition measures (glycosylated hemoglobin, blood pressure). Secondary analysis will descriptively measure effect size on ED visits and hospital admissions.

Hypotheses:

- 1A: OAA increases patient activation.
- 1B: OAA increases care plan adherence, including fewer no-shows and more on-time refills.
- 1C: OAA reduces Hgb A1c and BP

Aim 2: Assess the impact of open access audio on provider communication behavior and on their attention to patient contextual factors (i.e. individual Veterans needs and circumstances relevant to planning effective care).

Hypotheses:

- 2A: Providers obtain higher scores on measures of communication behavior when they know they are being recorded.
- 2B: Providers obtain higher scores on measures of attention to patient contextual factors essential to care planning when they know they are being recorded.

Aim 3: Assess patient, provider, and leadership perceptions of the extent to which the program is safe, not burdensome, and worthwhile at both the start and at two years into the program.

- Indicate the relevance to Veterans and the VA

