The superscripts associated with each outcome in the “How Answered” boxes in figure 2 refer to the following strategies for testing the hypotheses in Aims 1 and 2: (a) A survey called the Patient Activation Measure (PAM), (Appendix A-1) is completed by patient 1-2 weeks after their visit²²; (b) The “no show rate” is the inverse of Return Visit Adherence (RVA) rate;²³ (c) the Refill rate is “proportion of days covered” (PDC), a metric CMS utilizes in its plan ratings;²⁴ and (d) BP and HgB A1c are checked if they are repeated within 6 months; (e) The SEGUE Framework for evaluating and scoring communication behavior, as rated off of the audio recording by a research assistant utilizing a checklist (Appendix A-2)²⁵ and (f) Content Coding for Contextualization of Care, also called “4C”²⁶. Note: (b-d) are extracted from the CDW and SEGUE and 4C completed while accessing the medical record and listening to the audios. Finally, for all three arms, the members of the research team collecting the data and coding the audio are blinded as to study arm. There is no arm in which the patient is unaware a visit is audio recorded. Blinding the patient is not pertinent to achieving the aims of the study.

Figure 3, the flow diagram below, allocates patients in a parallel three arm randomized controlled trial (RCT) to most efficiently achieve the aims of the study (the calculations for the specific sample sizes are justified later in the protocol – and shown in Tables 4.1 and 4.2. on pp 24+25).

Figure 3: Flow diagram for parallel RCT

Random assignment to arms will be made using computer-generated sequences within the diabetes clinics (1:1 randomization to Arms 1 and 2 in blocks of 4) and primary care clinics (5:5:2 randomization to Arms 1, 2, and 3, in blocks of 24, with one partial block of 8 patients). Solid lines represent unconditional allocation of participants to Arms; dashed lines represent random sampling of participants to create efficient unbiased subsamples for key hypothesis tests. The rationale for the design, starting at the top of the figure and working down, is as follows:

- We start with two separate pools, diabetes and primary care clinics, because measurement of the effect of OAA vs control (Arm 1 vs Arm 2) on Hgb A1c is most efficiently accomplished

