Aim 1: Assess the impact of an open access audio program on two behaviors (patient activation, treatment plan adherence), two services (ED utilization, inpatient admissions), and two chronic condition measures (glycosylated hemoglobin, blood pressure).

Aim 1 hypotheses will be tested by comparing patients randomized to arms 1 (intervention) and 2 (control) on the outcomes specified in figure 2. Following an informed consent process (see "Informed Consent Procedures" p 20, below), the Veteran will carry an audio into the encounter, regardless of the arm to which they are assigned. They'll return the recorder when they leave. In Arm 1, the Veteran and provider will each be given access to a passcode to a website that will stream the audio from any internet enabled device. Audio is streamed rather than downloaded, to prevent inadvertent sharing. Also, with streaming, the platform can track for the research team whether, when, the number of times, and how long the audio is listened to by either party. In Arm 2 neither the Veteran nor provider will have access to the audio, but the research team can listen to it.

The decision to give the provider access to the audio whenever the patient has access is based on conversations with providers during the proposal planning process who have said they would not feel comfortable having a patient listen to a visit that they couldn't also listen to if they wished to do so. In Open Access Notes, both providers and patients have access to documentation of the visits, and so it seems logical that Open Access Audio should work in parallel, particularly given that current technology makes this feasible. The research team will be able to track whether and when either party access the audio. This will not contaminate isolating the impact of the audio on the patient (e.g. were the provider to call the patient after

listening to the audio to correct an error or elaborate), since we'll know when providers log in, enabling us to control for it as a co-variate or exclude if it's a rare event.

Aim 2: Assess the impact of open access audio on provider communication behavior and on their attention to patient contextual factors (i.e. individual Veterans' needs and circumstances relevant to planning effective care).

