As summarized in Table 4, we will apply several measures to assess the effectiveness of the intervention, testing hypotheses to achieve Aims 1 and 2. For each hypothesis, comparisons between arms will be made using mixed-effect linear or logistic regression as appropriate for the outcome, with a fixed effect of study arm, VA site, and primary vs. secondary care setting, and a random effect of provider to accommodate clustering of visits within providers. Of primary interest is the direction, magnitude, and significance of the regression coefficient associated with study arm. Primary analysis will compare arms on an intention-to-treat basis, without regard to whether audio made available in Arm 1 is actually accessed by anyone; secondary analyses will include covariates representing whether, how often, and by whom (patient or provider) audio is actually accessed in Arm 1 to assess the impact of audio use (vs. availability). As patients will be randomized to arms, we do not expect demographic or other patient differences among arms, but will conduct tests for differences, and if any variables differ significantly among arms, we will include them as covariates in the regression models.

Table 4. Hypotheses and evaluation strategy for effectiveness of intervention (Aims 1 and 2)

Hypothesis	Evaluation Strategy
1A: OAA increases patient activation.	Administer PAM (Appendix A-1) 1-2 weeks post visit via phone call and compare scores in Arm 1 vs. Arm 2
1B: OAA increases care plan adherence, including fewer no-shows and more on-time refills.	Utilizing the data warehouse measure Return Visit Adherence (RVA) and refill rates (PDC) ^{24,32,33} in Arms 1 vs. 2.
1C: OAA reduces Hgb A1c and BP	Same as above: Utilizing data warehouse measure A1c and BP.
2A: Providers obtain higher scores on measures of communication behavior when they know they are being recorded.	Completed by trained RA off of Audio: SEGUE checklist for communication completed by research team (Appendix A-2) ²⁵ , comparing randomly sampled visits in Arm 2 vs Arm 3.
2B: Providers obtain higher scores on measures of attention to patient contextual factors essential to care planning when they know they are being recorded.	4C for contextualization of care ³⁴ , comparing randomly sampled visits in Arm 2 vs Arm 3.

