As noted earlier, the PAM will be completed over the phone by the RA initially at one week after the visit (this will be extended to 10-14 days if it turns out a substantial number of patients listen to the audio more than one week after the visit).

Table 4.1 lists the calculated power for the intention-to-treat analyses for Hypotheses 1A-1C by outcome. These analyses are based on data from 1029 combined primary care and diabetes clinic visits each in Arms 1 and 2 (i.e. sample size 2058), except for measuring the effect of OAA on Hgb A1c (in 1C) which is based only on 202 diabetes clinic visits each in Arms 1 and 2 (total 404). For patient activation (1A), we assume veterans with no audio access will have a mean PAM score of 56 and standard deviation of 19.5, based on a 2016 national study of VA health care users;³⁵ clinically meaningful differences in activation have been described as 4-6 points.³⁶ Since testing hypothesis 1A requires a phone call to administer the PAM, we will randomly contact 924 participating subjects, an average of 9 calls/week across sites, which will achieve 80% power, instead of calling all 2058 subjects. Baseline rates of each undesirable outcome for 1B are derived from our previously published study in the VA using recordings without provider awareness or patient access (as in Arm 3), and we expect to find an odds ratio of 0.5 for each outcome when patients have access to audios.¹⁴ Baseline rates of each undesirable outcome for 1C are derived from the data warehouse (Chicago and Cleveland facilities – see table 3, above).

Table 4.1: Expected differences and power for planned intention-to-treat analyses for hypothesis 1A-1C

Hypothesis	Outcome	Baseline without audio available	Expected with audio available	Sample size	Power

		(Arm 2)	(Arm 1)	(total)	
1A	Patient activation (PAM 0-100 score)	56.0	60.0	924	80%
1B	Visit no-show rate	7%	4%	2058	95%
	Medication Proportion of days not covered	13%	7%	2058	80%
1C	Hgb A1c > 8 with repeat in < 6 Mo	66-70%	33-35%	404	80%
	Most Recent SBP>140 or DBP>90* with repeat in < 6 Mo	39%	24%	2058	99%

Also, while not included in Table 4.1, because it is not a primary objective of Aim 1, we will explore whether OAA is associated with fewer ED visits and hospitalizations. With the current sample size, we will in fact have 80% power to detect a decrease in inpatient admissions from 14%, the 2018 rate in our study population, to 9%.

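### The 80% power quoted for a fall in inpatient admissions from 14% to 9% is about 95% at the planned sample size, and one restatement of Aim 1 omits the secondary status of these outcomes

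*Combined protocol and SAP*

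**What the plan says.** The power statement is in section 5.6, directly after Table 4.1. The plan explains that ED visits and hospitalizations are left out of the table because they are not a primary objective of Aim 1, and that they will be explored. It then adds, for the sample size as it stands, "we will in fact have 80% power to detect a decrease in inpatient admissions from 14%, the 2018 rate in our study population, to 9"%. It gives no power figure for ED visits.

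The Arm 1 versus Arm 2 analyses rest on "1029 combined primary care and diabetes clinic visits each in Arms 1 and 2 (i.e. sample size 2058"). Allocation between these two arms is equal: "1:1 randomization to Arms 1 and 2 in blocks of 4" in the diabetes clinics and "5:5:2 randomization to Arms 1, 2, and 3, in blocks of 24" in primary care (section 5.1).

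On the status of these outcomes, section 3.0 says "Secondary analysis will descriptively measure effect size on ED visits and hospital admissions", and the Abstract says the same in substance. Section 5.1 restates Aim 1 when it describes the research activities. There it includes "two services (ED utilization, inpatient admissions") beside the behaviors and the chronic condition measures, without marking them as secondary.

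**The concern.** The power figure cannot be reproduced from the inputs printed with it. The sample size, both rates and the allocation are all in the documents, and together they imply power well above 80%. A reader who takes the sentence at face value will think the trial less sensitive to a change in admissions than it is, and would read a null result against the wrong benchmark.

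The second part is a labelling inconsistency. The section 5.1 wording of Aim 1 puts utilization on the same footing as the outcomes that have hypotheses, whereas the rest of the plan does not. If it stays, someone reporting a striking admissions result could cite section 5.1 to present it as a main Aim 1 finding.

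**Working it through.** **Inputs.** Control rate 0.14 and alternative 0.09 (section 5.6, after Table 4.1). Sample size 1029 per arm (section 5.6). Allocation 1:1 between Arms 1 and 2 (section 5.1). The analysis section refers to the "direction, magnitude, and significance of the regression coefficient associated with study arm" but gives no significance level or sidedness, so two-sided 5% is assumed. Complete data and no design effect are also assumed.

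**Does this formula suit the plan's other figures?** It reproduces both contextual rows of Table 4.2 when applied to the numbers of eligible visits that section 5.6 gives. Probing, 32% versus 47% with 168 per arm, comes to 80.6% (stated 80%). Planning, 59% versus 82% with 63 per arm, comes to 81.6% (stated 82%). Unadjusted two-sided 5% is therefore a fair reading of how at least those figures were obtained.

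**Attempt to reproduce the 80%.** Power = Φ{[|p1 − p2| − 1.96·√(2p̄(1 − p̄)/n)] / √([p1(1 − p1) + p2(1 − p2)]/n)}

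- p̄ = (0.14 + 0.09)/2 = 0.115, so 2p̄(1 − p̄) = 0.20355 and √(0.20355/1029) = 0.01406
- p1(1 − p1) + p2(1 − p2) = 0.1204 + 0.0819 = 0.2023, and √(0.2023/1029) = 0.01402
- (0.05 − 1.96 × 0.01406)/0.01402 = 1.60, and Φ(1.60) = **94.5%**

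The stated 80% is not reproduced.

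**Other methods, 1029 per arm:**

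| Method | Power |
|---|---|
| Continuity-corrected | 93.7% |
| Arcsine | 94.7% |
| Wald test on the log odds ratio | 94.2% |
| Fisher exact (simulated) | about 94% |
| One-sided 5% | 97.2% |

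Primary care patients alone (827 per arm) would give 89.1%.

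**What would give 80%?** The number per arm for 14% versus 9% is (1.96·√0.20355 + 0.8416·√0.2023)²/0.05² = 637.9, so 638 (678 with continuity correction). With 1029 per arm, 80% therefore needs one of these:

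- a design effect of about 1029/638 = 1.61;
- retention of 638/1029 = 62%, a loss of about 38%;
- a significance level of about 0.007 (0.05/7 gives 80.7%).

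The documents state none of them.

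**Rounding.** If the true rates lie anywhere in 13.5–14.5% and 8.5–9.5%, power runs from 81% to 99%. Only the corner of 13.5% versus 9.5% comes near 80% (81.2%).

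**Status.** The Abstract and section 3.0 call utilization a secondary, descriptive analysis. Section 5.6 calls it exploratory and not primary. Hypotheses 1A to 1C, Table 4 and Table 4.1 leave it out. Only the Aim 1 wording in section 5.1 lists it without qualification.

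**The case against.** The best defence of the 80% is that the planned model is not a simple two-proportion test. It includes "a random effect of provider to accommodate clustering of visits within providers" and covariates, and some loss of data is realistic. A design effect of 1.3 gives 87.7%, or 84.2% with a further 10% loss. A design effect of 1.5 with 10% loss gives 78.7%. These are assumptions, but they show that 80% could be a deliberately cautious figure. Several rows of Table 4.1 also fail to match the simple formula, which may point to an undisclosed method. Patient activation comes to 87.7% against 80% stated. The no-show rate comes to 84.8% against 95% stated (92.7% if the expected rate is taken as 3.63%, an odds ratio of 0.5 on 7%).

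Part of this stands: 95% is conditional on assumptions that the documents do not state. It does not rescue the sentence. Patients are randomized within clinics, so the same providers see patients in both arms, and clustering by provider should not by itself inflate the variance of the arm comparison by 1.6. Nor does one common design effect explain the table. At 1.6 the no-show power falls to 65.6% (76.9% with 3.63%), further from the stated 95%. If a cautious assumption was used, it needs to be written down.

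Two stronger readings are tempting. A reader might infer that the plan gives utilization three conflicting statuses, the last being a formal powered test. It does not. A secondary descriptive analysis and an exploratory one are compatible, and a remark on power for admissions alone does not make either outcome confirmatory. Even section 5.1 lists the outcomes without ranking them. A reader might also infer that 9% should simply become 10%, because 14% versus 10% gives 79.8%. That holds only with no design effect and no loss. With a design effect of 1.1 it is 75.9%, and with 1.3 it is 68.8%, so the edit would turn a conservative statement into an optimistic one.

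**Conclusion.** The concern holds as a minor correction. With 1029 per arm, two-sided 5%, complete data and no design effect, power for 14% versus 9% is about 94–95%, some 15 percentage points above the figure stated. The 80% has no basis in the documents as written. The discrepancy errs on the cautious side, concerns an exploratory outcome, covers admissions but not ED visits, and determines no sample size. The validity of the trial is not affected.

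The status inconsistency is confined to the Aim 1 statement in section 5.1. The rest of the plan already answers whether admissions are a main Aim 1 result: they are not.

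**What to change.** 1. **Section 5.6, after Table 4.1.** Either restate the power as about 95% for 14% versus 9%, with 1029 per arm, two-sided 5%, complete data and no design effect. Or keep 80% and state the significance level, sidedness, clustering allowance and attrition that produce it. In both cases give the follow-up window for admissions, since the documents give none and the 14% is a 2018 rate. Leave the 9% as it is.
2. **Section 5.1, Aim 1 statement.** Remove the two services from the list, or label them secondary and exploratory, so that it agrees with the Abstract, section 3.0 and section 5.6.

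The cost is two short text edits. Recruitment, data collection and the analysis model do not change.

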5.7 Withdrawal of Subjects

- Describe any anticipated circumstances under which subjects will be withdrawn from the research without their consent.

None

- Describe the consequences of a subject's decision to withdraw from the research and the procedures for orderly termination of participation by the subject (e.g., the subject contacting the investigator for an end-of-study visit).

No consequences. No consequences. For instance, if a patient decides that they don't want to record their visit, the just default to usual care.

- Describe procedures if a subject is withdrawn or withdraws from the intervention portion of the study but agrees to continue in the follow-up phases or for safety outcome purposes.

Not applicable. For instance, if a patient decides not to record their visit, there will be nothing to follow up.

6.0 Reporting

- Include procedures for reporting unanticipated problems, serious adverse events, and protocol deviations.

Any loss of research data (unsigned surveys submitted by physicians or patients), or notes related to focus group interviews will be reported to the IRB.

Any incident that could indicate the protocol adversely effects patient care or compromises patient privacy will prompt immediate suspension of the research.

If an SAE/UAP occurs during the course of the project, a Form 119 Report of Serious Adverse Events and Unanticipated Problems Involving Risks to Participants or Others will be filed with the CIRB. Information will be collected at the time of the incident or as soon as possible after the occurrence of the incident is made known to the study team **within the required 5 days**. Any incident impact the health or health care of a patient subject will be reported to their PCP in same time frame.

- All non-compliance with the study protocol or applicable requirements will be reported in accordance with VHA Handbook 1058.01. This will be achieved as follows:
 - The study team will discuss the importance of reporting non-compliance with the study protocol with all site investigators and will emphasize the importance of reporting non-compliance to the study team.
 - The PI/Study Coordinator will report instances of non-compliance in accordance with the VHA Handbook 1058.01.
 - If appropriate, the instance of non-compliance will be discussed between the study team and all site investigators to avoid duplication of non-compliance as well as to emphasize the importance of reporting non-compliance.
- Include information about whether the study has a Data Monitoring Committee and if so, how often it will meet.
 - Per requirement of HSR&D this project has been assigned to a VA Data Safety Monitoring Board (DSMB) since it is considered to be an interventional clinical trials. We have submitted and received approval for a Data Analysis Plan (DAP) to the DSMB via the ART website. The DSMB determined its own schedule for reviewing protocols based on VA ORS practices and policies.

7.0 Privacy and Confidentiality

- Describe whether the study will use or disclose subjects' Protected Health Information (PHI).

Patient PHI: The study will be collecting PHI, consisting of audio recordings of encounters and patient email addresses, to send them links to their audio files. As noted above, the data analyst will extract the patient outcomes and demographic data from the Central Data Warehouse. He will have access to PHI briefly as he runs search in the Corporate Data Warehouse.

For data tracking purposes, we will create a master spreadsheet with a row for each patient encounter. A code will be assigned to each encounter linked to a cross-walk file (see below).

The three patient surveys (literacy survey, exit survey, and patient activation measure) will be handled similarly: they will be assigned an encounter specific code, with a link to the cross-walk file.

Provider Subject PHI: Survey and focus group data is not PHI. However it is possible that during an employee focus group discussion about the OAA project, that a clinician could mention a patient's name or other identifier. This is not likely as the topic of the focus groups is the OAA project not the care of any specific individual.

- Describe the steps that will be taken to secure the data (e.g., training, authorization of access, password protection, encryption, physical controls, Certificates of Confidentiality, and separation of identifiers and data)

The data encryption and storage methods are highly secure, but are monitored for safety using standard software storage review processes, including log analysis.

All study team members will be required to maintain necessary research training, and the PI of the study team will oversee completion and maintenance of any required training.

The cross-walk file will be kept in a separate file from the master file, accessible only with permission from the PI with access enabled by the IT data manager. Access is based exclusively on need, as follows: The data analyst who access the CDW to look up A1c and BP, RVA and PDC; The RA who completes the PAM 1-2 weeks post visit; and the RA who completes the SEGUE and completes the 4C coding, both off the audio.

The research records and data will be stored and destroyed in compliance with record Control Schedule (RCS) 10-1.

